# APPENDIX B. QOL-PCD ADOLESCENT (13-17 YEARS) SCORING ALGORITHM (VERSION 2.0)

Blue figures: as coded in eCRF; blue box: items to be re-coded

QOL-PCD QUESTIONNAIRE	lescents Age	ents Ages 13 to 17 years					
Section I. Quality of Life							
Please check the box indicating your answer.							
During the past week, to what extent have you had difficulty:	A lot of difficulty	Some difficulty	A little difficulty	No difficulty			
1. Performing activities such as running or playing sports	1	2	3	4			
2. Walking as fast as others	1	2	3	4			
3. Climbing stairs as fast as others	1	 2	3	4			
During the past week, indicate how often:	Always	Often	Sometimes	Never			
4. You felt well	1	 	3	4			
5. You felt worried about getting sick	□ 1	□ 2	3	□ 4			
6. You felt happy	1	□ 2	□ 3	□ 4			
7. You felt tired	1	□ 2	3	□ 4			
8. You felt energetic	1	 	3	4			
9. You felt exhausted	1	 	3	4			
10. You felt sad	1	1 2	3	4			
11. Your treatments for PCD got in the way of your activities	<pre>1</pre>	2	3	4			
12. Doing your treatments frustrated you	<pre>1</pre>	□ 2	3	4			
Thinking about the state of your health over the last week:  13. How difficult is it for you to fit in your treatments (including medications) each da  1. Not at all 4 re-coding not needed 2. A little 3 as correctly done at	ay?						

CONFIDENTIAL Page 96 of 139

QOL-PCD QUESTIONNAIRE	Adolescents Ages 13 to 17 years			
Please select a box indicating your answer.				
Thinking about your health during the past week, indicate the extent to which each sentence is true or false for you.	Very True	Mostly True	Somewhat True	Not At All True
14. I have trouble recovering after physical effort	🔲 1	□ 2	□ 3	□ 4
15. I have to limit activities such as running or playing sports	🗖 1	□ 2	□ 3	□ 4
16. I feel comfortable discussing my illness with others	🔲 1	 	 3	4
17. I feel comfortable blowing my nose in front of friends	. 🔲 1	 	 3	4
18. People are afraid I might get them sick.	🔲 1	2	 3	 4
19. I think my coughing bothers others.	🔲 1	2	 3	4
20. It is difficult to make plans for the future (for example, going on in school, getting a job, etc.)		□ 2	□ 3	□ 4
Section II. School, Work, or Daily Activities				
21. How often were you absent from school, work, or unable to complete daily activit or treatments?  ☐ Always 1 ☐ Often 2 ☐ Sometimes 3	ies during the	•	because of y	our illness
22. To what extent does PCD get in the way of meeting school, work, or your own goal A lot 1 Moderately 2 A little 3	als?	1 4		

CONFIDENTIAL Page 97 of 139

QOL-PCD QUESTIONNAIRE Adolescent	s Ages 13 to 17 years
----------------------------------	-----------------------

Section III. Symptoms  Please select a box indi	icating your	answer.		
Indicate how you have been feeling during the past week.	A great deal	Somewhat	A little	Not at all
23. Have you been congested in the chest?	1	2	 3	□ 4
24. Have you been coughing during the day?	□ 1	2	□ 3	4
25. Have you had to cough up mucus (including swallowing it)?	1	2	3	4 If not at all go to Question 27
During the past week:				
26. Has your mucus been mostly: □Clear 1 □Clear to yellow	2	☐Yello	owish-green	3
☐Greenish 4 ☐Green with traces	of blood 5	□Don't	t know	6
27. You had fluid coming out of your ears	A great deal	Somewhat	A little	Not at all 4
28. You had trouble hearing (if you wear hearing aids: you had trouble hearing without your aids)	□ 1	□ 2	□ 3	□ 4
29. You felt snot dripping down your throat	1	2	□ 3	4
During the past week, indicate how often:	Always	Often	Sometimes	Never
30. Your breathing has been noisy (whistling, wheezy chest)	. 🗖 1	2 2	□ 3	□ 4
31. You had a stuffy nose	$\square$ 1	□ 2	□ 3	□ 4
32. You had difficulty sleeping because of your chest			□ 3	
33. You had trouble breathing				
34. Your ears hurt	1	2 2	□ 3	4
35. You had a runny nose	□ 1	□ 2	□ 3	1 4
36. You had difficulty sleeping because your nose was blocked up	. 🔲 1	2	□ 3	4
37. Your ears were blocked up	🔲 1	2	 3	4
38. Von had a headache				

CONFIDENTIAL Page 98 of 139

### **Calculation of domain scores**

Each of the 38 items is scored from 1 to 4, except item #26 which is score from 1 to 6, with higher scores representing fewer symptoms or better functioning and quality of life. The CRF of this study is partly designed that reverse coding is applied and is not necessary for all items as detailed in the "General Hand Scoring Instructions" for the QOL-PCD Adolescent Version 2 questionnaire. Please check the questionnaire items above. Each item highlighted in blue bar will require reverse coding.

Before calculating the scale scores, the following preparations are necessary:

- If item 25 = 4 (Not at all) then item 26 is set to missing
- If item 26 = 6 (Don't know) then item 26 is set to missing

### **Scale scores**

Each of the 9 domain scores is standardized on a 0 to 100-point scale with higher scores representing fewer symptoms or better functioning and quality of life.

Scale scores are derived from a subset of items and calculated by

$$scale\ score = \frac{sum\ of\ responses - minimum\ possible\ sum\ (n*1)}{maximum\ possible\ sum\ (n*4) - minimum\ possible\ sum\ (n*1)}*100$$

While n is equal to the number of items (questions) in the respective scale. Contributing items are given in Table 13 below:

Table 13: QoL-PCD Items Contributing to Domain Score Calculation

Domain	#items	Contributing items	Allowed #missing items*
Physical Functioning	5	1, 2, 3, 14, 15	2
Emotional	4	4*, 5, 6*, 10	2
Functioning			
Treatment Burden	3	11, 12, 13*	1
Role	3	20, 21, 22	1
Social Functioning	4	16*, 17*,18, 19	2
Vitality	3	7, 8*, 9	1
Upper Respiratory	5	29, 31, 35, 36,38	2
Symptoms			
Lower Respiratory	7	23, 24, 25, 26*, 30, 32,	3
Symptoms		33	
Hearing Symptoms	4	27, 28, 34, 37	2

\*If more missing items are observed than allowed, the domain will not be scored.

**Example**: For a scale compromising four items (n=4), such as the Emotional Functioning scale, the calculation method is for a participant who obtains 7 points (e.g., 2 points for item #4, 2 points for item #6, and 1 point for item #10):

scale score = 
$$\frac{7 - (4 * 1)}{(4 * 4) - (4 * 1)} * 100 = 25$$

CONFIDENTIAL Page 99 of 139

# APPENDIX C. QOL-PCD CHILD (12 YEARS) SCORING ALGORITHM (VERSION 2.0)

Blue figures: as coded in eCRF; blue box: items to be re-coded

QOL-PCD QUESTIONNAIRE	Children Ages 6-12 years			
Please check the box matching your response.				
In the past week:	Very True	Mostly True	A little bit True	Not at all True
1. You were able to walk as fast as others	1	 	 3	4
2. You were able to climb stairs as fast as others	1	□ 2	□ 3	□ 4
3. You were able to run, jump, and climb as you wanted	1	 2	3	4
4. You were able to run as quickly and as long as others	1	□ 2	 3	□ 4
5. You were able to do sports that you enjoy (e.g., soccer, dancing or others)	1	 2	3	 4
Please check the box matching your response.				
And during this past week, indicate how often:	Always	Often	Sometimes	Never
6. You felt mad	1	 2	3	4
7. You felt grumpy	□ 1	□ 2	 3	4
8. You felt worried about getting sick	1	 2	3	4
9. You felt sad	1	 	3	4
10. You felt frustrated about doing your daily treatments	□ 1	□ 2	 3	1 4
11. You had to stop having fun to do your treatments	1	□ 2	 3	4

CONFIDENTIAL Page 100 of 139

QOL-PCD QUESTIONNAIRE	Children Ages 6 to 12 years
-----------------------	-----------------------------

Please check the box matching your response.					
During the past week:	Very True	Mostly True	A little bit True	Not at all True	
12. You were late or missed school because of PCD	1	□ 2	3	4	
13. You had enough time to do all of your treatments		□ 2	 3	$\square_4$	
14. Doing treatments in front of your friends bothers you	1	□ 2	3	4	
15. You spent a lot of time with your friends	□ 1	□ 2	3	□ 4	
16. You missed going to after-school activities because of PCD		 2	$\square_3$	□ 4	
17. You were teased by other children because your nose was runny.		D 2	 3		
18. Others were afraid you would get them sick	1	□ 2	3	4	
19. You had trouble hearing (if you wear hearing aids: you had trouble hearing without your aids)	□ 1	□ 2	3	4	
20. Doing your treatments bothered you	<pre>1</pre>	2	3	4	
21. Your ears felt blocked up	<pre>1</pre>	□ 2	3	4	
Please check the box matching your response.					
Let us know how often in the past week:	Alwa	ys Often	Sometimes	Never	
22. You coughed during the day	🗆	1 🗖	2 🗖 3		1
23. Your ears hurt		1 🗖	2 🗖 3		1
24. You woke up during the night because you were coughing	🗆	1 🗖	2 🔲 3	□ 4	1
25. You had to cough up mucus (even if you swallow it)		1	2 🔲 3	 	1

CONFIDENTIAL Page 101 of 139

QOL-PCD QUESTIONNAIRE Children Ages 6 to	o 12 yea	rs					╛
Let us know how often in the past week:	Always	Often	So	metin	ies	Never	
26. You had trouble breathing	□ 1		2		3		4
27. You had liquid coming out of your ears	$\square_1$		2		3		4
28. You woke up during the night because your nose was blocked up	□ 1		2		3		4
29. Your chest hurt	□ 1		2		3		4
30. You had mucus stuck in your chest	1		2		3		4
31. You had a runny nose	1		2		3		4
32. Your head hurt (near your eyes or in your forehead)	1		2		3		4
33. Your nose felt blocked up	1		2		3		4
34. You felt snot (stuff) dripping down your throat	1		2		3		4

Handling of missing items and calculation of the domain scores are detailed in the below table. Calculation of the score is identical to adolescents as detailed in Appendix B.

Table 14: QoL-PCD Child Items Contributing to Domain Score Calculation

Domain	#items	Contributing items	Allowed #missing items+
Physical Functioning	5	1*, 2*, 3*, 4*, 5*	2
Emotional Functioning	4	6, 7, 8, 9	2
Treatment Burden	5	10, 11, 13*, 14, 20	2
Social Functioning	5	12, 15*, 16, 17,18	2
Upper Respiratory	5	28, 31, 32, 33, 34	2
Symptoms			
Lower Respiratory	6	22, 24, 25, 26, 29, 30	3
Symptoms			
Hearing Symptoms	4	19, 21, 23, 27	2

+If more missing items are observed than allowed, the domain will not be scored.

CONFIDENTIAL Page 102 of 139

\*Reverse coding: 1=4, 2=3, 3=2, 4=1

# APPENDIX D. QOL-PCD PARENT/CAREGIVERS (CHILDREN AGES 6 TO 12 YEARS) SCORING ALGORITHM (VERSION 2.0)

Blue figures: as coded in eCRF; blue box: items to be re-coded

QOL-PCD QuestionnaireParents/Caregivers (Children Ages 6 to 12)						
Section I. Quality of Life  Please indicate how your child has been feeling during the past week by checking the box matching your response.						
To what extent has your child had difficulty:	A lot of Some A little No difficulty difficulty difficulty					
1. Performing vigorous activities, such as running or playing sports						
2. Walking as fast as others	2 3 4 1					
3. Climbing stairs as fast as others	2 3 3 4 0					
4. Climbing several flights of stairs	2 0 3 0 4 0					
During the past week, indicate how often your child:	Always Often Sometimes Never					
5. Seemed happy	2 3 4 0					
6. Seemed worried about his/her illness	- 2 - 3 - 1 -					
7. Seemed tired	···					
8. Seemed well	··· D 2 D 3 D 4 D					
9. Seemed energetic						
10. Was absent or late for school or other activities because of his/her illness of						
treatments						
Please check the box that matches your response to these questions.  Thinking about your child's state of health during the past week, indicate the extent to which each sentence is true or false for your child:  Very Mostly Somewhat Not at						
	true true True all True					
2. My child had trouble recovering after physical effort	□ 2 □ 3 □ 4 □					
3. Mealtimes were a struggle	□ 2 □ 3 □ 4 □					
4. My child's treatments got in the way of his/her activities	2 3 4 0					
5. My child felt healthy	2 3 4 0					
My child got enough help in his/her classroom to perform well (e.g., sitting up front, time to make up homework when sick)	2 3 4 5					
7. My child was able to keep up with his/her school work or outdoor activities1	2 3 4 5					
8. My shild count a lot of time on his/her treatments arounday.						

CONFIDENTIAL Page 103 of 139

### QOL-PCD QuestionnaireParents/Caregivers (Children Ages 6 to 12)

Please circle the number indicating your answer. Please choose only one answer for each question.

- 19. How difficult is it for your child to fit in his/her treatments (including medications) each day? 1 Not at all
- 2 2. A little
- 3. Moderately
- 4 4. Very
  - 20. How do you think your child's health is now?
- 1 l. Excellent
- 2 2. Good
-  3. Fair
- 4. Poor

### Section II. Symptoms

Please indicate how your child has been feeling during the past week.

	Ā	deal	Son	newha	ıt	A little		Not at all
21. My child had trouble gaining weight	1		2		3		4	
22. My child's ears hurt	1		2		3		4	
23. My child's chest was congested	1		2		3		4	
24. My child coughed during the day	1		2		3		4	
25. My child had to cough up mucus (including swallowing it)	1		2		3		4	
26. My child had a runny nose	1		2		3		4	
27. My child felt mucus dripping down his/her throat	1		2		3		4	

Page 104 of 139 **CONFIDENTIAL** 

During the past week:	Always	Often	Sometimes	Never
28. My child had trouble hearing (if aided, he/she had trouble without aids)	1 🔲	2 🔲	3 🗖	4
29. My child had fluid draining from his/her ears	 $\square$	2	3	4
30. My child had a sinus headache	1 🗖	2	3	4
31. My child had trouble breathing	1 □	2 🗖	3 🗖	4
32. My child woke up during the night because he/she was coughing	1 🗖	2 🗖	3 🗖	4
33. My child had a stuffy nose	1 $\square$	2 🗖	3	4
34. My child's chest hurt	1 🔲	2 🔲	3 🗖	4
35. My child had a poor appetite	1 🗖	2 🗖	3	4

Handling of missing items and calculation of the domain scores are detailed in the below table. Calculation of the score is identical to adolescents as detailed in Appendix B.

Table 15: QoL-PCD Patent/Caregiver Items Contributing to Domain Score Calculation

Domain	#items	Contributing items	Allowed #missing items+
Physical Functioning	5	1, 2, 3, 4, 12	2
Emotional Functioning	3	5*, 7, 9*	1
Treatment Burden	4	11, 14, 18, 19*	2
Social Functioning	3	10, 16*, 17*	1
Eating and Weight	3	13, 21, 35	1
Health Perception	4	6, 8*, 15*, 20*	2
Upper Respiratory	4	26, 27, 30, 33	2
Symptoms			
Lower Respiratory	6	23, 24, 25, 31, 32, 34	3
Symptoms			
Hearing Symptoms	3	22, 28, 29	1

+If more missing items are observed than allowed, the domain will not be scored.

CONFIDENTIAL Page 105 of 139

\*Reverse coding: 1=4, 2=3, 3=2, 4=1

# APPENDIX E. BRONCHIECTASIS EXACERBATION AND SYMPTOM TOOL

Symptoms reported using the BEST diary consists of 6 symptoms: breathlessness, fatigue, sputum volume, sputum color, cough, and cold and flu symptoms. Total possible BEST score for all symptom ratings ranges from 0 to 26. Participants were asked to complete the BEST questionnaire (in the evening) on an electronic diary DAILY from the Screening Visit through EOS Visit (Week 56).

The calculation of the BEST score is the sum of symptom responses, e.g., 1+1+1+1+1+1=6 for responses: "Breathless when hurrying or walking up a hill", "I feel a little tired", "Less than a teaspoon", "White", "Mild" and "Sore throat, sore muscle, or runny nose". If 50% or more of symptom responses are missing, e.g., 3 or more, the BEST score will not be calculated.

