#### 6.7.5.3. Bronchiectasis Exacerbation and Symptoms Tool (Adults only)

The BEST Diary will be completed every day and a score will be calculated for each daily entry. BEST Diary Baseline Score is defined as average of BEST Diary daily scores from screening to Study Day 1 (inclusive). The daily change from Baseline in BEST score over the 52-week treatment period will be calculated for each participant as the individual daily change from baseline. In addition, a BEST Diary Score (overall post-baseline) will be calculated, defined as the average of all the non-missing BEST Diary daily score for a given participant post-baseline.

BEST data will also be averaged over 4-week periods in a table and figure.

Calculation of the BEST score is detailed in Appendix E.

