### 6.9.1. Missing PRO Administrations and Missing Item Responses

Missing individual item PRO responses will not be imputed.

Domain scores will be calculated as per corresponding PRO manual, the derivations are described within corresponding variable section. In case the domain score is not evaluable, it will be treated as missing and will follow the rules specified for missing data handling described within the corresponding efficacy section.

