**Table 16: BEST Items Contributing to BEST Score Calculation** 

Bro	eathlessness	Fatigue		
0	None or rarely	0	I do not feel tired	
1	Breathless when hurrying or walking up	1	I feel a little tired	
	a hill			
2	Have to walk slowly on level ground or	2	I feel tired but can still do the things I	
	stop for breath after a few minutes on		would like to do	
	level ground			
3	Can walk less than 100m or a few	3	Tiredness is stopping me from doing	
	minutes on level ground before having		things I want to do	
	to stop			
4	Breathless when washing or dressing	4	I am so tired I am unable to carry my	
			usual daily activities	
Sp	utum Volume	Sputum Color		
0	No sputum	0	No sputum	
1	Less than a teaspoon	1	White	
2	Teaspoon to an egg-cup	2	Yellow	
3	Egg-cup to a cup	3	Green	
4	More than a cup	4	Dark Green	
5		5	Blood stained	
Co	Cough		ld and Flu Symptoms	
0	None	0	None	
1	Mild	1	Sore throat, sore muscle, or runny nose	
2	Moderate	2	Fever/high temperature	
3	Severe	3		
4	Very severe	4		
5		5	I feel like I have an infection	

CONFIDENTIAL Page 106 of 139

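### A daily BEST score with one or two unanswered items is a plain sum, so each missing item counts as symptom-free and the day's score is understated

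*SAP*

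**What the plan says.** - **Items and range.** SAP Appendix E: "Symptoms reported using the BEST diary consists of 6 symptoms" and "Total possible BEST score for all symptom ratings ranges from 0 to 26".
- **Formula.** Appendix E: "The calculation of the BEST score is the sum of symptom responses". The worked example has six responses of 1, totalling 6.
- **Partial entries.** Appendix E: "If 50% or more of symptom responses are missing, e.g., 3 or more, the BEST score will not be calculated". One or two missing responses do not stop the score being calculated.
- **Imputation.** SAP Section 6.9.1: "Missing individual item PRO responses will not be imputed".
- **Meaning of 0.** In SAP Table 16 the lowest response to every item is absence of the symptom; for breathlessness it reads "None or rarely".
- **Use of the score.** SAP Section 6.7.5.3 says that "a score will be calculated for each daily entry". Baseline is the mean of daily scores from screening to Study Day 1, and the overall post-baseline score is the mean of the non-missing daily scores. Section 8.5.1 analyses average daily change from baseline by ANCOVA. It also plots change by study day and for 21 days either side of PE onset, and summarises 4-week averages.

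Neither Section 6.7.5.3 nor protocol Section 7.5.1 gives any other rule for a partly completed entry.

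**The concern.** The formula, the threshold and the ban on imputation are each unremarkable alone. Together they give a wrong daily score. Leaving an item out of a sum gives the same total as entering 0, and 0 is the best answer on every BEST item. The SAP does not say that a skipped symptom is scored as absent, but that is the result of the calculation it specifies.

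The same SAP avoids this for QoL-B. Appendix A takes the mean of the answered items before scaling to 0 to 100, so a permitted missing item does not pull the score towards one end.

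At stake is the accuracy of exploratory objective 1. The display around PE onset deserves particular care: if items are skipped more often on bad days, the omitted values are then at their largest and the peak is flattened.

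**Working it through.** **1. The SAP's own figures.** Item maxima in Table 16 are breathlessness 4, fatigue 4, sputum volume 4, sputum colour 5, cough 4, cold and flu 5. Their sum is 4 + 4 + 4 + 5 + 4 + 5 = 26, as stated. Half of six items is 3, as stated. The example gives 6 x 1 = 6, as stated.

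**2. Error on one day.** Scored value minus true value = -(sum of the true values of the missing items). The loss is 0 to 5 points for one item and 0 to 5 + 5 = 10 for two.

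| True responses | True score | One missing | Two missing |
|---|---|---|---|
| All 1 (SAP example) | 6 | 5 | 4 |
| All 2 | 12 | 10 | 8 |
| All at maximum | 26 | 21 to 22 | 16 to 18 |

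A mixed day of 2, 2, 2, 3, 2, 0 in Table 16 order has a true score of 11. Without the two sputum items it scores 11 - (2 + 3) = 6. That is the most costly pair; the average loss over all 15 pairs is 11 x 5/15 = 3.7.

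**3. Error in a period mean.** Let f be the share of scored days that are partial, and v the mean true total of the missing items on those days. The period mean is shifted by -f x v. The documents give neither quantity. Assuming f from 0% to 20%, one or two items missing, and a mean item value of 1 to 2 (so v from 1 to 4), the shift runs from 0 to -0.20 x 4 = -0.8 points. This is a shift in level, not a treatment effect.

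**4. Error in change from baseline.** The same scoring applies in both periods, so the error is -(f x v after baseline) + (f x v in screening). For a participant whose true score is always 12, with one item of value 2 skipped daily:

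- skipped only after baseline: 10 - 12 = -2, a false improvement;
- skipped only in screening: 12 - 10 = +2, a false worsening;
- skipped in both: 10 - 10 = 0.

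**5. Error in the arm comparison.** Only a between-arm difference in step 4 matters. Two illustrations, both assumptions:

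- Partial days differ by 2 percentage points between arms, with v = 5: 0.02 x 5 = 0.1 point.
- Partial days are 10% in both arms, with v = 4 on placebo and 3 on active: 0.4 - 0.3 = 0.1 point. Placebo is lowered more, so a true benefit shrinks.

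**6. Rescaling by the maxima of the answered items.**

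- Mixed day above: answered sum 6, answered maxima 26 - 4 - 5 = 17, score 26 x 6/17 = 9.2, against 6 under the SAP and 11 in truth.
- All responses 1, one missing: 26 x 5/22 = 5.9 or 26 x 5/21 = 6.2. Two missing: from 26 x 4/18 = 5.8 to 26 x 4/16 = 6.5. Truth is 6.
- All at maximum: always 26. By contrast, multiplying the mean answered item by 6 can reach 27.0, because item maxima differ.

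**7. Scoring complete days only.** Take a usual score of 8, with 10% of days truly 18 and two items worth 6 skipped on those days (assumption).

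- True mean: 0.9 x 8 + 0.1 x 18 = 9.0.
- SAP rule: 0.9 x 8 + 0.1 x 12 = 8.4.
- Complete days only: 8.0.
- Rescaled: the bad day scores from 26 x 12/18 = 17.3 to 26 x 12/16 = 19.5, so the mean is 8.9 to 9.2.

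**The case against.** The strongest reply is that the practical effect may be nil. BEST is completed on an electronic device, and the documents do not say whether an item can be left blank. If the device enforces completion, f is 0 and nothing changes. This stands as a limit on size. It does not remove the error from the written rule, because Appendix E provides for partial entries and so treats them as possible.

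A second reply is that Section 6.9.1 refers to the instrument manuals, which might prorate. However, that section points to the SAP for the derivations, and the BEST derivation there contains no proration.

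A third is that the error need not bias the comparison. This stands. Baseline is scored by the same rule, and similar skipping in blinded arms shifts all arms about equally. If skipping is concentrated on bad days, the arm with more bad days is understated more; if the drug works, that is placebo, and the bias is towards no effect.

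A reader might infer that participants will generally appear improved, or that the rule favours brensocatib. The documents support neither: the direction depends on when items are skipped, and nothing in them suggests skipping that differs by arm. Nor do they support a wider inference that PE counts are affected. PEs rest on protocol-defined symptoms, a physician's antibiotic decision and adjudication, and nothing links the diary's alert algorithm to the Appendix E score.

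**Conclusion.** The point holds as a scoring error of unknown practical size. Any day with one or two missing items is understated by the true value of those items, by at most 5 or 10 points respectively on a 26-point scale. This follows from the SAP text and needs no assumption.

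The effect on a period mean, 0 to about 0.8 points, rests on assumed partial-day shares of 0% to 20% and item values of 1 to 2. The effect on the treatment comparison requires an understatement that differs by arm, through either the frequency of skipping or the severity of the skipped items; it was 0.1 point in each illustration.

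The reach is limited to exploratory objective 1 and its summaries and plots. BEST is outside the six families in SAP Section 6.3.1, so the primary endpoint and the multiplicity-controlled secondary endpoints are untouched.

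**What to change.** In SAP Appendix E, state that when one or two of the six responses are missing, the daily score is 26 x (sum of answered items) / (sum of the maxima of the answered items). Apply this identically to screening, baseline and post-baseline days. Keep the rule that no score is calculated with three or more missing.

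Also report the number of partial days by arm and period, which would show whether the point matters in practice.

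The cost is one sentence and a small change to the derivation. It should be made before unblinding, because SAP Section 1 treats analyses added afterwards as post hoc. The downside is that rescaling assumes the missing items are about as severe, relative to their maxima, as the answered ones.

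A complete-days-only version can serve as a sensitivity check. It should not be the main rule: step 7 of the working shows that it can be further from the truth than the present rule when items are skipped on bad days.
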